**3 September 2024**

**Summary of Changes from Previous Version:**

Affected Section(s)	Summary of Revisions Made	Rationale
Throughout	Addition of UNIFESP as an enrollment center for REAGIR II: increasing REAGIR II target enrollment to 60, and including prednisolone acetate 1% as study drug	
Section 9	Added Bayesian Analysis	

## STATEMENT OF COMPLIANCE

The trial will be carried out in accordance with International Conference on Harmonisation Good Clinical Practice (ICH GCP) and the following:

- United States (US) Code of Federal Regulations (CFR) applicable to clinical studies (45 CFR Part 46, 21 CFR Part 50, 21 CFR Part 56, 21 CFR Part 312, and/or 21 CFR Part 812)

National Institutes of Health (NIH)-funded investigators and clinical trial site staff who are responsible for the conduct, management, or oversight of NIH-funded clinical trials have completed Human Subjects Protection and ICH GCP Training.

The protocol, informed consent form(s), recruitment materials, and all participant materials will be submitted to the Institutional Review Board (IRB) for review and approval. Approval of both the protocol and the consent form must be obtained before any participant is enrolled. Any amendment to the protocol will require review and approval by the IRB before the changes are implemented to the study. In addition, all changes to the consent form will be IRB-approved; a determination will be made regarding whether a new consent needs to be obtained from participants who provided consent, using a previously approved consent form.

## 1 PROTOCOL SUMMARY

### 1.1 SYNOPSIS

**Title:** Steroids and Cross-linking for Ulcer Treatment (SCUT II), Rose Bengal Electromagnetic Activation with Green light for Infection Reduction (REAGIR), and Rose Bengal Electromagnetic Activation with Green light for Infection Reduction II (REAGIR II)

**Study Description:** The Steroids and Cross-linking for Ulcer Treatment (SCUT II) and Rose Bengal Electromagnetic Activation with Green light for Infection Reduction (REAGIR) trials are international, randomized, double-masked, sham and placebo-controlled, clinical trials; and Rose Bengal Electromagnetic Activation with Green light for Infection Reduction II (REAGIR II) is a randomized, double-masked feasibility study. The purpose of these studies is to determine differences in 6-month visual acuity between medical antimicrobial treatments alone versus antimicrobial treatment plus corneal cross-linking (CXL), as well as to further evaluate findings from subgroup analyses of SCUT.

### SCUT II

Patients presenting to one of the Aravind Eye Hospitals in India, to the University of California San Francisco (UCSF), or to Bascom Palmer Eye Institute at the University of Miami with smear-positive typical (i.e. non-*Nocardia* or *Mycobacteria*) bacterial corneal ulcers and moderate to severe vision loss, defined as Snellen visual acuity of 20/40 or worse, will be eligible for inclusion. Those who agree to participate will be randomized to one of three treatment groups:

- Group 1, Standard therapy: topical 0.5% moxifloxacin plus topical placebo plus sham UVX
- Group 2, Early steroids: topical 0.5% moxifloxacin plus topical difluprednate 0.05% plus sham UVX
- Group 3, UVX plus early steroids: topical 0.5% moxifloxacin plus topical difluprednate 0.05% plus UVX

### REAGIR

Patients presenting to one of the Aravind Eye Hospitals in India or to the Federal University of São Paulo in Brazil (UNIFESP) with either smear or culture positive fungal or acanthamoeba keratitis or smear and culture negative corneal ulcers and moderate to severe vision loss, defined as Snellen visual acuity of 20/40 or worse, will be eligible for inclusion. Those who agree to participate will be randomized to one of two treatment groups:

- Group 4, Sham RB-PDT: topical chlorhexidine gluconate 0.02%/PHMB 0.02% (acanthamoeba), moxifloxacin 0.5% (smear/culture negative) or natamycin 5%/Amphotericin B 0.15% (fungal keratitis) plus sham RB-PDT
- Group 5, RB-PDT: topical chlorhexidine gluconate 0.02%/PHMB 0.02% (acanthamoeba), moxifloxacin 0.5% (smear/culture negative) or natamycin 5%/Amphotericin B 0.15% (fungal keratitis) plus RG-PDT

### REAGIR II

Patients presenting to one of the Aravind Eye Hospitals in India or to the Federal University of São Paulo in Brazil (UNIFESP) with smear-positive and/or culture positive typical (i.e. non-*Nocardia* or *Mycobacteria*) bacterial corneal ulcers and moderate to severe vision loss, defined as Snellen visual acuity of 20/40 or worse, will be eligible for inclusion. Those who agree to participate will be randomized to one of two treatment groups:

- Group 6, RB-PDT Plus Early Steroids: topical 0.5% moxifloxacin plus topical difluprednate 0.05%/prednisolone acetate 1% plus RB-PDT
- Group 7, Sham RB-PDT Plus Early Steroids: topical 0.5% moxifloxacin plus topical difluprednate 0.05%/prednisolone acetate 1% plus sham RB-PDT

### Objectives:

**Specific Aim 1: To determine if corneal cross-linking with riboflavin (UVX) is a beneficial adjuvant in the treatment of smear- and/or culture-positive bacterial ulcers.**

- a. We anticipate that UVX will result in better best spectacle corrected visual acuity (BSCVA) at 6 months compared with antibiotic alone.
- b. We anticipate that UVX will result in faster microbiological cure rates, smaller scar size and lower rate of corneal perforation compared with antibiotic alone.

**Specific Aim 2: To determine if early topical steroids are a beneficial adjuvant in the treatment of smear- and/or culture-positive bacterial ulcers.**

- a. We hypothesize that those randomized to early topical steroids will have improved BSCVA at 6 months compared with antibiotic alone.

**Specific Aim 3: To determine which ulcer characteristics predict the most benefit from the addition of adjuvant corneal cross-linking and/or early steroids.**

- a. We hypothesize that culture positive bacterial ulcers with drug resistant organisms, as measured by MIC50, will benefit more from adjuvant UVX than those with antibiotic susceptible organisms.

**Specific Aim 4: To determine if cross linking with rose bengal (RB-PDT) is a beneficial adjuvant in the treatment of fungal, acanthamoeba, and smear or culture negative corneal ulcers.**

- a. We hypothesize that there will be improved visual acuity at 6 months among those randomized to adjuvant RB-PDT after controlling for baseline visual acuity.
- b. We anticipate that there will be smaller infiltrate/scar size and decreased rate of perforation and/or need for TPK at 6 months among RB-PDT treated patients.

**Specific Aim 5: To determine if corneal cross-linking with rose bengal (RB-PDT) is a beneficial adjuvant in the treatment of smear- and/or culture-positive bacterial ulcers.**

- a. We hypothesize that study participants treated with topical antibiotics plus adjunctive RB-PDT will have better best spectacle corrected visual acuity at 6 months compared to those treated with antibiotics alone.

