## 9 STATISTICAL CONSIDERATIONS

### 9.1 STATISTICAL HYPOTHESES

**Specific Aim 1: To determine if corneal cross-linking with riboflavin (UVX) is a beneficial adjuvant in the treatment of smear- and/or culture-positive bacterial ulcers.**

- a. We anticipate that UVX will result in better best spectacle corrected visual acuity (BSCVA) at 6 months compared with antibiotic alone.
- b. We anticipate that UVX will result in faster microbiological cure rates, smaller scar size and lower rate of corneal perforation compared with antibiotic alone.

**Specific Aim 2: To determine if early topical steroids are a beneficial adjuvant in the treatment of smear- and/or culture-positive bacterial ulcers.**

- a. We hypothesize that those randomized to early topical steroids will have improved BSCVA at 6 months compared with antibiotic alone.

**Specific Aim 3: To determine which ulcer characteristics predict the most benefit from the addition of adjuvant corneal cross-linking and/or early steroids.**

- a. We hypothesize that culture positive bacterial ulcers with drug resistant organisms, as measured by MIC50, will benefit more from adjuvant UVX than those with antibiotic susceptible organisms.

**Specific Aim 4: To determine if cross linking with rose bengal (RB-PDT) is a beneficial adjuvant in the treatment of fungal, acanthamoeba, and smear or culture negative corneal ulcers.**

- a. We hypothesize that there will be improved visual acuity at 6 months among those randomized to adjuvant RB-PDT after controlling for baseline visual acuity.
- b. We anticipate that there will be smaller infiltrate/scar size and decreased rate of perforation and/or need for TPK at 6 months among RB-PDT treated patients.

**Specific Aim 5: To determine if corneal cross-linking with rose bengal (RB-PDT) is a beneficial adjuvant in the treatment of smear- and/or culture-positive bacterial ulcers.**

- a. We hypothesize that study participants treated with topical antibiotics plus adjunctive RB-PDT will have better best spectacle corrected visual acuity at 6 months compared to those treated with antibiotics alone.

Primary Endpoint: Best spectacle-corrected visual acuity at 6 months

- Prior to publishing the SCUT II primary outcomes, optometrist experts will be surveyed regarding the outcomes of the study for a Bayesian analysis. The results of the questionnaire will serve as the prior when performing Bayesian analysis of the clinical trial results.

Secondary Endpoints:

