## 9.2 SAMPLE SIZE DETERMINATION

**Sample Size Calculation for SCUT II Primary Analysis: BSCVA.** We power the study for each pairwise comparison. Specifically, we will be comparing (Specific Aim 1) CXL plus early steroids (arm 3) versus steroids and sham cross linking (arm 2), and (Specific Aim 2) early steroids with sham CXL (arm 2) versus standard therapy (arm 1). The power calculation was based on the primary outcome, 6-month BSCVA. We informed the calculation with measurements from the first Steroids for Corneal Ulcers Trial (SCUT), among patients enrolled with between 20/60 and 20/400 vision. The SCUT trial measured BSCVA at baseline, 3-months, and 12-months. We conservatively used the 12-month outcome measure for the calculations since there was no 6-month measurement. The standard deviation of BSCVA at 12 months was 0.293. Since the primary analysis will adjust for baseline BSCVA, we used an estimate of the residual standard deviation, which is  $SD_r = SD\sqrt{1 - r^2}$ , where  $r$  is the correlation between the baseline measure and primary endpoint. In SCUT, the correlation between baseline and 12-month BSCVA among patients with between 20/60 and 20/400 vision at enrollment was 0.216. We thus assumed a residual standard deviation of  $0.293\sqrt{1 - 0.216^2} = 0.286$ . Assuming a significance level of  $0.05/2=0.025$ , and allowing for approximately 15% loss to follow up, we estimate that we will have 80% power to detect a 1.4-line difference (logMAR 0.14) between groups with 93 study participants per arm (279 total). This calculation applies to each of the two prespecified primary outcomes for this trial (corresponding to the two separate research questions), and is based on the standard power formula for the T-test (using an estimated residual standard deviation). Note that if the trial were to enroll 60 patients per arm, the minimum detectable effect under all the same assumptions would be 1.8 lines (logMAR 0.18). See SCUT II SAP Section 1.5.6 for details on interim power analysis.

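### For 6-month BSCVA, hypotheses 1a and 5a name antibiotic alone as the comparator, but the available contrasts estimate cross-linking added to antibiotic plus early steroid

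*Protocol*

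**What the plan says.** Hypothesis 1a (Protocol 1.1 Objectives and 9.1) reads: "We anticipate that UVX will result in better best spectacle corrected visual acuity (BSCVA) at 6 months compared with antibiotic alone". Hypothesis 5a says that participants given topical antibiotics plus RB-PDT "will have better best spectacle corrected visual acuity at 6 months compared to those treated with antibiotics alone". Section 9.1 repeats 5a as a formal statistical hypothesis, beginning "We hypothesize that study participants treated with topical antibiotics plus adjunctive RB-PDT will have better best spectacle corrected visual acuity at 6 months". Section 4.1 echoes both, under SCUT II and REAGIR II. The purpose statement in 1.1 and 4.1 also sets antimicrobial treatment alone against antimicrobial treatment plus cross-linking.

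SCUT II (1.1) has one arm without steroid, listed as "Group 1, Standard therapy: topical 0.5% moxifloxacin plus topical placebo plus sham UVX". Its only cross-linked arm does include steroid: "Group 3, UVX plus early steroids: topical 0.5% moxifloxacin plus topical difluprednate 0.05% plus UVX". The remaining arm, which has steroid but no active cross-linking, is "Group 2, Early steroids: topical 0.5% moxifloxacin plus topical difluprednate 0.05% plus sham UVX".

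In REAGIR II, Group 7 receives "topical 0.5% moxifloxacin plus topical difluprednate 0.05%/prednisolone acetate 1% plus sham RB-PDT". Group 6 receives the same drugs with active RB-PDT.

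Section 9.2 ties Specific Aim 1 to "CXL plus early steroids (arm 3) versus steroids and sham cross linking (arm 2". Section 9.4.1 fits a separate model to Groups 2 and 3, after first describing a model with one indicator for steroid and one for cross-linking. For Aim 5, no supplied text names the contrast. With only two groups, it can only be 6 versus 7.

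**The concern.** The hypotheses promise an effect of cross-linking against antibiotic alone. The contrasts deliver an effect of cross-linking in patients who are all on antibiotic and steroid. The two agree only if steroid does not modify the effect of cross-linking.

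The protocol's own rationale gives reasons to doubt that. Section 2.1 suggests that UVX may cut organism burden at once and so make later anti-inflammatory treatment safer, which would make cross-linking more useful alongside steroid. Sections 2.1 and 2.2 also credit cross-linking with an anti-inflammatory action, which could overlap with steroid and make it less useful there.

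A positive result for Group 3 versus 2, or 6 versus 7, reported in the words of 1a or 5a would therefore be unsupported. A related risk concerns the expert survey that 9.1 plans as the prior for a Bayesian analysis of SCUT II. No contrast is named for it. If the experts were asked in the words of 1a, the prior would describe a different effect from the one the data estimate.

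**Working it through.** **1. Which contrast the plan's figure belongs to.** Inputs from Protocol 9.2: SD 0.293, correlation 0.216, difference 0.14 logMAR, two-sided alpha 0.025, power 80%, loss 15%, 93 per arm.

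- Residual SD = 0.293 × √(1 − 0.216²) = 0.286.
- Evaluable n per arm = 2 × (2.241 + 0.842)² × 0.286² / 0.14² = 79.3, so 80.
- Enrolled: 80 / 0.85 = 94.1, so 95; or 80 × 1.15 = 92. The stated 93 lies between.
- In reverse, 93 × 0.85 = 79 evaluable gives power of 79.8% (normal) or 79.1% (t).

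The figure reproduces, and 9.2 attaches it to arm 3 versus arm 2, both on steroid. The power statement concerns the right contrast.

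**2. What each arm identifies.** Let s = 1 if steroid is given and c = 1 if cross-linking is given, all on antibiotic. Write mean 6-month BSCVA as β0 + β1·s + β2·c + β3·s·c.

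| Arm | s | c | Mean |
|---|---|---|---|
| Group 1 | 0 | 0 | β0 |
| Group 2 | 1 | 0 | β0 + β1 |
| Group 3 | 1 | 1 | β0 + β1 + β2 + β3 |
| Group 7 | 1 | 0 | β0 + β1 |
| Group 6 | 1 | 1 | β0 + β1 + β2 + β3 |

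The parameters are specific to each trial; the table shows only the form.

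- Literal 1a or 5a, cross-linking plus antibiotic against antibiotic alone: β2.
- Group 3 − 2, and Group 6 − 7: β2 + β3.
- Group 2 − 1 (Aim 2): β1.
- Group 3 − 1: β1 + β2 + β3. This is estimable but changes two treatments at once, and it is not a planned primary contrast.

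The SCUT II arm matrix has rank 3 for 4 parameters. β2 and β3 occur only as a sum, so β2 is not estimable. REAGIR II identifies β2 + β3 and nothing relative to antibiotic alone.

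**3. Whether the two-indicator model helps.** The model that opens 9.4.1 has no interaction term, so it sets β3 = 0. Across three arms, an intercept and two indicators already fit the arm means exactly. The data therefore cannot show whether β3 = 0 is wrong.

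**4. An illustration, on assumed values.** Suppose Group 3 beats Group 2 by the design difference of 1.4 lines. The benefit without steroid is then 1.4 − β3, with β3 in lines of benefit. The documents give no value for β3. Taking −1.4, 0 and +1.4 as assumptions, the benefit against antibiotic alone is 2.8, 1.4 or 0 lines. The trial data would be the same in all three cases.

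**The case against.** The plan is clearer than the hypotheses suggest. The aim headings ask whether cross-linking is a useful adjuvant, and the objectives table in section 3 speaks only of its effect on BSCVA. Section 9.2 names the Aim 1 contrast correctly, and the group names show the steroid. The supplied SAP covers REAGIR only, and the separate SCUT II and REAGIR II SAPs mentioned in 9.4.1 may be precise. All of this stands, and it leaves the SCUT II analyst in no doubt about the primary BSCVA contrast. It does not repair the formal hypotheses in 9.1, and for Aim 5 nothing supplied corrects them.

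Three stronger readings are tempting and are not supported:

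- *The contrasts are invalid or the aims untestable.* They are not. Group 3 versus 2 and Group 6 versus 7 are sound randomised comparisons of cross-linking on a steroid background.
- *Every comparator for bacterial ulcers receives steroid.* Microbiological cure (9.2, 9.4.2) and the Aim 3 drug-resistance analysis (9.2) compare Group 3 with Groups 1 and 2 pooled, and Group 1 has no steroid. Section 9.2 also places the repeat culture before any antibiotic, so the cure analysis does not test 1a either.
- *The investigators plan to claim superiority over antibiotic alone from these contrasts.* No passage says so. The risk is that the stated hypothesis invites it. REAGIR II is also described as a feasibility study of 60 participants, which limits what Aim 5 could support.

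**Conclusion.** The point holds for 6-month BSCVA in hypotheses 1a and 5a, which belong to two of the four primary aims (1, 2, 4 and 5 in section 3). The stated comparator is antibiotic alone; the estimable effect is cross-linking added to antibiotic plus early steroid. The first follows from the second only under an assumption of no steroid-by-cross-linking interaction, which the supplied documents do not state and neither design can test.

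This is an error in the hypotheses and in the conclusion they would license. It is not an error in randomisation, sample size or the BSCVA contrast. Its size cannot be put as a number, because the interaction is unknown; the range in the illustration rests on assumed values. The conclusion rests on the arm definitions in the supplied protocol. The SCUT II and REAGIR II SAPs could not be checked, but they cannot make β2 estimable from these arms.

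**What to change.** Reword hypotheses 1a and 5a in Protocol 1.1 and 9.1, and their echoes in 4.1, to: *cross-linking added to antibiotic plus early topical steroid, compared with antibiotic plus early topical steroid plus sham*. Limit the BSCVA conclusions for Aims 1 and 5 to that contrast. Align the purpose statement in 1.1 and 4.1. Its present framing suits REAGIR, whose study regimens contain no steroid, so the change should be specific to SCUT II and REAGIR II.

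Do not apply the new wording to Aim 1 as a whole. State the comparator for 1b endpoint by endpoint: microbiological cure keeps Groups 1 and 2 pooled, scar size follows the pairwise comparisons in 9.4.2, and perforation needs its contrast named, since 9.4.2 gives none. Leave the Aim 3 drug-resistance analysis with its pooled comparator.

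The cost is a protocol wording change and a narrower claim. No arm, sample size or analysis changes. Section 1.1 describes SCUT II as closed to enrollment, so for Aim 1 the change affects only the stated hypothesis and the reported conclusion. The amendment log can record it as a clarification, because 9.2 and 9.4.1 already specify Group 3 versus Group 2.

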**Endpoints:**

Primary Endpoint: Best spectacle-corrected visual acuity at 6 months

Secondary Endpoints:

- Microbiological cure on repeat smear and culture at Day 2
- Interaction of minimum inhibitory concentration (MIC) and CXL on best spectacle-corrected visual acuity
- Infiltrate/scar size/depth, as measured by clinical exam, clinical photographs, Pentacam and OCT at week 3 and months 3, 6, and 12
- Adverse events including rate of perforation/need for TPK
- BSCVA at Day 1, 3 weeks, 3 months, and 12 months
- Astigmatism, higher order aberrations, topography, and densitometry as measured on Pentacam at week 3 and months 3, 6, and 12

- Corneal thickness and scar size/depth as measured by AS-OCT at week 3 and months 3, 6, and 12
- Basal nerve plexus, white blood cell count, and keratocyte density on confocal microscopy at week 3 and months 3, 6, and 12
- Visual function questionnaire (VFQ) will be compared between groups at 6 months, controlling for Day 1 VFQ
- Pain scale at baseline, Day 1, and Day 3
- Subgroup analysis of study participants receiving prior topical antimicrobial therapy

**Study Population:**

Participants with bacterial corneal ulcers (SCUT II n= 279; REAGIR II n = 60) and 330 participants with fungal, acanthamoeba, or smear/culture negative corneal ulcers (REAGIR) will be enrolled at Aravind Eye Hospitals in Coimbatore, Madurai, Pondicherry, and Tirunelveli in Tamil Nadu, South India, at the Federal University of São Paulo, Brazil, at the University of California San Francisco, USA, and at the University of Miami. We anticipate that participants from India will be native to India, an ethnic group often reported as “South Asian”. Previous studies at Aravind suggest that approximately 39-50% of presenting ulcers will be in women. At UCSF, patients will be a mixture of White (non-Hispanic), Hispanic, African-American, and Asian, and will be an estimated 50% female. The original SCUT trial had a median age of 53 years, with interquartile range of 40-61 years, and we expect a similar age range in this study. Participants from Bascom Palmer Eye Institute will be patients that live in South Florida and the Caribbean islands around South Florida. South Florida has a mixture of Hispanic patients, White (non-Hispanic), and African American. Previous studies from Bascom Palmer have had a patient population younger than the SCUT trial. Participants from Brazil will be a mixture of White (non-Hispanic), Hispanic, African American, and Asian, and will be an estimated 50% female. Our most recent epidemiological study of infectious keratitis cases at Hospital São Paulo at the Federal University of São Paulo showed that the population had a mean age of  $48 \pm 21$  years, and we expect a similar age range in this study.

Phase:	N/A
Description of Sites/Facilities Enrolling Participants:	Participants will be enrolled at four sites in India, one site in Brazil, and two sites in the United States. In India, participants will be enrolled at Aravind Eye Hospitals in Tamil Nadu: Coimbatore, Madurai, Pondicherry, and Tirunelveli. Patients will be enrolled at the Cornea Clinic in each hospital. In the United States, participants will be enrolled at the Proctor

Foundation clinic at the University of California, San Francisco in San Francisco, CA, and at Bascom Palmer Eye Institute at the University of Miami in Miami, FL. In Brazil, participants will be enrolled at Hospital Sao Paulo, the University hospital of Escola Paulista de Medicina at the Federal University of Sao Paulo (Universidade Federal de Sao Paulo – UNIFESP).

